# **Data analysis**

For hospital, ward and patient demographic variables, descriptive and summary statistics will be presented. CPE prevalence estimates will be calculated overall and also presented by strata. Associations between colonisation or infection with CPE and hypothesised risk factors data will also be analysed using univariable, and if required, multivariable analysis. Results will be stratified by ICU-type, with odds ratios, p-values and 95% CI. All analysis will be done using Stata 15.1.

Anonymised results from the survey may be used to inform additional CPE/CPO assessments to understand the impacts of AMR in line with the National Action Plan.

#### Patient consent

Existing regulations provide UKHSA with the legal option to process patient data without direct patient consent. The transfer of data to UKHSA and processing of said data will be conducted within information governance standard. Personal data on the population studied will be kept and handled in compliance with the Caldicott Principles.

UKHSA will manage the secure and encrypted transfer of data through the online data collection tool.

All data, including personally identifiable information, (forename, surname, NHS number, date of birth) will be kept confidential and retained in compliance with UK laws and the Caldicott principles. An anonymised dataset will be kept for use in modelling studies.

### **Practical considerations**

# **Timeline**

- Mid-July 2021 finalisation of protocol and survey questions
- January to February 2022 develop training materials
- February 2022 contact hospitals selected for inclusion in survey
- March 2022 training for survey leads
- April 2022 conduct survey in hospitals
- May to July 2022 data analysis
- August 2022 produce report of results

September was determined to be the most sensible month for conducting this survey as it lies outside winter and winter pressures. However, the timeline was moved in response to the COVID-19 pandemic, with the next best option for conducting the survey being in the Spring.

# **Expected benefits**

# Output

The main output of this survey will be the production of a report outlining the results. This will be made available to stakeholders both within PHE and within the NHS. It is also anticipated that a journal article and a conference presentation regarding the findings will be produced. An anonymised dataset will be produced for use in modelling interventions.

#### **Outcome**

This work will improve our knowledge of CPE in intensive care, and will provide further support for the development of monitoring and surveillance of these organisms in England. Journal articles and conference presentations will help to provide further evidence of the burden of these organisms to key stakeholders.

# Appendix 1 – survey questions CPE PPS questions

\*Minimum (mandatory) dataset

#### The following data will be collected once per trust

Field name	Field description	Response
Trust code	Unique Trust code	System generated
*Reporting organisation	Trust name	Single select drop- down/system-filled
*Date survey commenced		DD-MM-YYYY
*What age groups are you submitting data on?		Multiselect drop-down: Adults Paediatrics
		Neonates
*Is there a CPE screening policy in operation at the trust?	Asked once per age group	Single select drop-down: Yes No
		Unknown
*What is the CPE screening policy at the trust?	Asked once per age group	Multiselect drop-down:  All admissions High-risk admissions High-risk areas Known CPE carriers Contacts of cases Other
If "other" screening policy, please specify	Provide details of screening policy in operation at Trust	Text
*Number of ICU beds	Number of ICU beds in the trust for the age range sampled	Integer
	Asked once per age group	

#### The following data will be collected once per unit

Field name	Field description	Response
ICU code	Unique study code for ICU	System assigned
*Reporting organisation	ICU name	Single select drop-down
*Date survey commenced	Chosen date of survey	DD-MM-YYYY
*ICU type	Specialty of ICU	Multiselect drop-down:
		Adult
		General medical General surgical Specialty
		Paediatric
		General medical
		General surgical
		Specialty
		Neonatal NICU Neonatal HDU
ICU specialty type	Specify type of ICU if "Specialty"	Text
*Care level	What levels of care are provided	Multiselect drop-down: Level 3 Level 2
*Compliance with CPE	Estimate how often	Single select drop-down:
screening policy	screening policy is	Almost never
	complied with at time of survey completion	Sometimes
		Often
		Almost always Unknown

*Awareness of CPE Framework of Actions	Indicate the level of awareness of the PHE document 'Framework of actions to contain carbapenemase-producing Enterobacterales'	Single select drop-down:  Very few staff  Some staff  Most staff  Almost all staff  Unknown
*CPE screening frequency	Frequency of CPE screening	Multiselect drop-down: Admission Weekly Outbreak Known CPE carrier Other
If "other" screening frequency, please specify	Provide detail of screening frequency is "other"	Text
*Are antibiotic stewardship guidelines in place on the ward?		Single select drop-down: Yes No Unknown
*Number of beds	Number of NHS-funded beds on ward	Integer
*Bed occupancy	Number of beds occupied on the date of the survey	Integer

#### The following data will be collected once per patient

The following data should be answered in relation to the date as referenced in the list below.

Note only one date is required, please complete for the first that is applicable as working down the list

- 1. Date of screening test (if single test)
- 2. If multiple screening tests:
  - a. If any positive, date of first positive screen OR
  - b. If all negative, date of most recent screen
- 3. Today's date if never screened

Field name	Field description	Response/notes				
Patient details						
Patient ID	Unique patient ID	System generated				
*Reporting organisation	ICU name	Single select drop down				
*Date of interest	Date of interest to which exposure questions relate. In order of preference:	DD-MM-YYYY				
	1. Date of CPE screening test (if single test) 2. If multiple CPE screening tests: a. If any positive, date of first positive screen OR b. If all negative, date of most recent screen					
	3. Today's date if never screened					
*10-digit NHS number	10-digit NHS number, if not available, enter [contact]					
*Forename	Patient first name	Text				
*Surname	Patient surname	Text				
*Date of birth	Patient date of birth	DD-MM-YYYY, if not known enter 01/01/1900				
*Sex	Biological sex	Button options:				
		Male Female Unknown				
Patient details 2						
*Survey date	Date survey is conducted	DD-MM-YYYY				
*Patient age group		Single select drop-down: Adults				
		Paediatrics				
		Neonates				

Ethnicity	Ethnicity of patient	Two-stage single select drop-down
*UK resident	Indicate if patient normally resides in the UK  NB. If for a neonate, please use details of mother	Single select drop-down: Yes No Unknown
Normal country of residence if not UK		Single select drop-down
*Birthweight	Birth weight (in grams) of neonatal patients i.e. babies less than 28 days old OR on NICU.	Number in grams
*Gestation	Gestation for babies aged under 1 year	Weeks + days
*Patient category	Indicate patient category on admission	Single select drop-down: NHS Private Diplomatic Other Unknown
Other patient category	Specify patient category if "other"	Text
*Date admitted to hospital	Date admitted to the trust, or date of birth if neonate and admitted since birth	DD-MM-YYYY
*Admitted from	Setting patient admitted from into the trust	Single select drop-down:  Home  A&E International transfer Nursing home Other Trust  Non-NHS hospital Non-health-related institute Temporary accommodation Other
Other admitted from	Specify if admitted from "other" location	Text

*Date admitted to ICU	Date admitted to ICU	DD-MM-YYYY
Time admitted to ICU	Specify time admitted to ICU	HH:MM (24-hour clock)
*Location admitted to ICU from	Setting patient admitted from into ICU	Single select drop-down: Home A&E HDU within same Trust Other ward within same Trust International transfer Nursing home Other Trust
		Non-NHS hospital Non-health-related institute Temporary accommodation Other Unknown
Other admitted from (ICU)	Specify if admitted to ICU from "other" location	Text
*If admitted to ICU from another ward within the same Trust, please specify	Specify specialty patient was admitted into the ICU from	Single select drop down Adult Paeds Neonates Other
If other, please specify	Specify other/specialty	Text
Please specify Adult speciality		
 
General medical
 
General surgical
 
Specialty
 
Intensive care
 

Please specify Paeds speciality		

Medical

Surgical

Specialty

Intensive care

		

Surgical

Specialty

	Γ	T
If 'Speciality', please specify which Paeds speciality	Specify other/specialty	Text
If 'Speciality', please specify which Neonatal speciality	Specify other/specialty	Text
APACHE II score	Score measures severity of disease for patients admitted to ICUs. Provide score assigned to patient on admission to ICU	Integer, ranging 0 - 71
Microbiology details		
*Was this patient tested for CPE, either as screening or as part of clinical investigations?		Single select drop-down: Yes No Unknown
*Was it a screening or clinical specimen?	Indicate if screening specimen or clinical specimen	Single select drop-down: Screening Clinical Unknown
*Date CPE specimen collected	Date specimen collected (if single specimen). If multiple specimens, please provide the most recent date.	DD-MM-YYYY
Specimen/laboratory number assigned to specimen		Free text
Indicate anatomical site specimen collected if clinical specimen		Single select drop-down
*Organism	Organism isolated associated with CPE positive result. If no result yet, select "Unknown/result awaited". If no organism isolated, select "No organism isolated".	Single select drop-down

	T	T
Does phenotypic testing indicate the presence of a carbapenemase?	Indicate if phenotypic (antibiotic susceptibility) testing indicates presence of a carbapenemase	Single select drop-down: Yes No Unknown
Indicate which carbapenemase family was detected (select all that apply)	Indicate which carbapenemase family was detected (select all that apply)	Multiselect drop-down
If Other, specify other carbapenemase family		Text
Screening (NB no additional sc	reening is required)	
*CPE on admission to Trust	Was the patient known to be CPE positive on admission to Trust	Single select drop-down: Yes – colonised Yes - infected No Unknown
*CPE screening on admission to Trust	Found to be CPE positive on admission to Trust.  "Yes" if screening specimen positive, "no" if screening specimen negative, "unknown" if no screen performed.	Single select drop-down: Yes No Unknown
*CPE on admission to ICU	Known to be CPE positive on this admission to ICU i.e. communicated/identified at time of admission.	Single select drop-down: Yes No Unknown
*ICU screen required	Did patient meet requirement to be screened for CPE on ICU in accordance with your policy?	Single select drop-down: Yes No Unknown
*ICU admission screen	Was patient screened for CPE on this admission to ICU?	Single select drop-down: Yes No Unknown

		1
*ICU admission screen date	Date admission screen was taken on ICU	DD-MM-YYYY
*Result of ICU admission screen	Indicate result from ICU CPE admission screen	Single select drop-down: Positive Negative Unknown
*Previous CPE	Indicate if patient known to be CPE colonised/infected in 12 months prior to first day of survey	Single select drop-down: Yes – colonised Yes - infected No Unknown
If previous history of CPE, specify date of most recent positive result.	Provide date of most recent CPE positive result (prior to ICU admission screen, if taken)	DD-MM-YYYY
Previous contact with CPE	Indicate if in contact with known CPE case during this admission	Single select drop-down: Yes No Unknown
Healthcare exposure		
*UK non-NHS hospital admission in previous 12 months	Any hospital admissions to non-NHS hospitals in the previous 12 months	Single select drop-down: Yes No Unknown
Specify UK non-NHS hospital admission	Provide name(s) of non- NHS hospitals admitted to in previous 12 months	Free text
*Healthcare overseas in previous 12 months	Any hospital admissions overseas in 12 months prior to admission at Trust	Single select drop-down: Yes No Unknown
Specify healthcare abroad	List countries where overseas healthcare received in previous 12 months	Multiselect dropdown of countries

*Healthcare worker  Travel exposure	Includes working in hospitals, care/nursing homes, hospices	Single select drop-down: Yes No Unknown
*Overseas travel in previous 12 months (if known)	Any overseas travel in 12 months prior to admission to Trust	Single select drop-down: Yes No Unknown
*Specify overseas travel	List countries travelled to in previous 12 months	Multiselect dropdown of countries
Family travel	Any family members within the same household as patient travel in the previous 12 months	Single select drop-down: Yes No Unknown
Specify family travel	List countries where family members travelled in previous 12 months	Multiselect dropdown of countries
Interventions		
*Has the patient undergone major surgery since admission to the Trust, on or prior to the date of interest?	Surgery is defined as a procedure where an incision is made (not just a needle puncture), with breach of mucosa and/or skin (not necessarily in an operating theatre). If the patient has had more than one surgery since admission, report the most recent surgery.	Single select drop-down: Yes No Unknown
*Surgery date	If yes, date of surgery	DD-MM-YYYY
*Has the patient undergone endoscopy since admission to the Trust, on or prior to the date of interest?	If yes, surgery type Undergone endoscopy during this admission, prior to date of interest	Free text  Single select drop-down:  Yes  No Unknown

*Endoscopy date	If yes, date of most recent endoscopy	DD-MM-YYYY
Endoscopy type	If yes, specify type of endoscopy	Single select drop-down:  Colonoscopy Sigmoidoscopy Upper endoscopy/ Esophagogastroduodenosc opy (EGD) Endoscopic retrograde cholangiopancreatography (ERCP) Percutaneous endoscopic gastrostomy (PEG) Other
*Is the patient currently receiving Chemotherapy	Is the patient currently receiving chemotherapy for cancer treatment, or received chemotherapy in the four weeks prior to the date of interest	Single select drop-down: Yes No Unknown
Specify chemotherapy indication (select all that apply)		Single select drop-down:  Oral, nasal and pharyngeal Oesophagus Stomach Colorectal Hepatobiliary Respiratory Larynx Lung Breast Female reproductive Prostate Testicular Renal Urinary bladder Bone and joint Melanoma Non-melanoma skin Soft-tissue sarcoma Brain Leukaemia (other than

		chronic B-cell leukaemia) Chronic lymphocytic (including hairy cell leukaemia) Other
Chemotherapy indication if other		Free text
*Is the patient currently receiving renal haemodialysis	Receiving regular renal haemodialysis or received haemodialysis in the four weeks prior to the date of interest	Single select drop-down: Yes No Unknown
* Is there at least one CVC in situ on date of interest?	Indicate if the patient had a CVC in place at the date of interest	Single select drop-down: Yes No Unknown
CVC date	If yes, when was it inserted. If multiple, select the insertion date of the CVC which has been in situ the longest.	DD-MM-YYYY
*Was a CVC in situ the day before the date of interest?	If no, indicate if the patient had a CVC in place the day before the date of interest	Single select drop-down: Yes No Unknown
Is there at least one PVC in situ on date of interest?	Indicate if the patient had a PVC in place at the date of interest	Single select drop-down: Yes No Unknown
PVC date	If yes, when was it inserted. If multiple, select the insertion date of the PVC which has been in situ the longest.	DD-MM-YYYY
Was a PVC in situ the day before the date of interest?	If no, indicate if the patient had a PVC in place the day before the date of interest	Single select drop-down: Yes No

		Unknown
Is there a urinary catheter in situ on the date of interest?	Indicate if the patient had a urinary catheter in place at the date of interest	Single select drop-down: Yes No Unknown
Urinary catheter date	If yes, when was it inserted	DD-MM-YYYY
Urinary catheter previously	If no, indicate if the patient had a urinary catheter in place in the 48 hours before the date of interest	Single select drop-down: Yes No Unknown
*Intubation	Indicate if the patient was under intubation with or without ventilation (endotracheal/nasotracheal tube or tracheostomy) at the date of interest	Single select drop-down: Yes No Unknown
Intubation date	If yes, when was it inserted	DD-MM-YYYY
*Intubation previously	If no, indicate if the patient was intubated in the 48 hours before the date of interest	Single select drop-down: Yes No Unknown
Nasogastric tube	Indicate if the patient had an NGT in place at the date of interest	Single select drop-down: Yes No Unknown
Nasogastric tube date	If yes, when was it inserted	DD-MM-YYYY
Nasogastric tube previously	If no, indicate if the patient had an NGT in place in the 48 hours before the date of interest	Single select drop-down: Yes No Unknown
Antimicrobials		
*Has the patient received carbapenems in the four	Indicate if the patient received carbapenems in	Single select drop-down: Yes

weeks prior to the date of interest?	the four weeks prior to the date of interest	No Unknown
If yes, which?	Carbapenems	Multiselect drop-down Doripenem Ertapenem Faropenem
		Imipenem
		Imipenem with cilastin Imipenem with cilastin and relebactam
		Meropenem  Meropenem/vaborabactam
*Has the patient received carbapenems in the one year prior to the date of interest, but not in the four weeks prior?		Single select drop-down: Yes No Unknown
If yes, which	Carbapenems	Multiselect drop-down
*Has the patient received 3rd generation cephalosporins in the four weeks prior to the date of interest?		Single select drop-down: Yes No Unknown
If yes, which	3rd generation cephalosporins	Multiselect drop-down
*Has the patient received 3rd generation cephalosporins in the one year prior to the date of interest, but not in the four weeks prior		Single select drop-down: Yes No Unknown
If yes, which	3rd generation cephalosporins	Multiselect drop-down
*Antimicrobials prescribed and taken on the date of interest	Indicate if the patient has received at least one	Single select drop-down:

	systemic antibiotic on the date of interest (given or planned treatment, including intermittent treatments, e.g. alternate day or medical prophylaxis). For surgical prophylaxis, check whether any surgical prophylaxis was given in the 24 hours before 8 a.m. on the day of the survey. If "yes", collect antibiotic data.	Yes No Unknown
Please select the number of antimicrobials taken		Single select drop-down:  1  2  3  4  5
*Antimicrobial name 1-5  NOTE: Field repeated up to 5 times depending on the specified number of antimicrobials taken	Select which antimicrobial	Single-select dropdown list of antimicrobials.
*Antimicrobial indication 1-5  NOTE: Field repeated up to 5 times depending on the specified number of antimicrobials taken	Please give indication for this/these antimicrobial(s)	CI = treatment of community-acquired infection LI = treatment of infection acquired in long-term care facility (e.g. nursing home) HI = treatment for acute hospital-acquired infection SP = surgical prophylaxis MP = medical prophylaxis O = other indication UI = unknown indication (confirmed) UNK = unknown or missing information

	T	T
*CPE indication for antimicrobial 1-5  NOTE: Field repeated up to 5 times depending on the specified number of antimicrobials taken	Is this antibiotic prescribed to manage CPE?	Single select drop-down: Yes No Unknown
Start date for antimicrobial 1-5  NOTE: Field repeated up to 5 times depending on the specified number of antimicrobials taken	Start date of the antibiotic.  If the antibiotic was already given on admission to hospital, provide the date of admission.	DD-MM-YYYY.
Antibiotic stewardship 1-5  NOTE: Field repeated up to 5 times depending on the specified number of antimicrobials taken	Is antibiotic prescription in line with local guidelines	Single select drop-down: Yes No Unknown
*Antimicrobials prior to the date of interest	Indicate how many antimicrobial(s) received since admission to hospital, but stopped prior to the date of interest. If more than 5 antimicrobials were prescribed, please enter details for the most recent 5.	Single select drop-down: Yes No Unknown
*Please select the number of antimicrobials taken this admission, prior to the date of interest	Indicate if antimicrobial(s) received since admission, prior to date of interest	Single select drop-down: 1 2 3 4 5
*Antimicrobial name 1-5 (prior survey)	Select the antimicrobial received since admission, prior to date of interest	Single-select dropdown list of antimicrobials.

		1
NOTE: Field repeated up to 5 times depending on the specified number of antimicrobials taken		
*Indication for antimicrobial 1-5 (before date of interest)  NOTE: Field repeated up to 5 times depending on the specified number of antimicrobials taken	Please give indication for this/these antimicrobial (s)	CI = treatment of community-acquired infection LI = treatment of infection acquired in long-term care facility (e.g. nursing home) HI = treatment for acute hospital-acquired infection SP = surgical prophylaxis MP = medical prophylaxis O = other indication UI = unknown indication (confirmed) UNK = unknown or missing information
*CPE indication for antimicrobial 1-5 (before date of interest)	Is this antimicrobial prescribed to manage CPE?	Single select drop-down: Yes No Unknown
NOTE: Field repeated up to 5 times depending on the specified number of antimicrobials taken		
Start date for antimicrobial 1-5 (before date of interest)	Start date of the antimicrobial. If the antimicrobial was already	DD-MM-YYYY
NOTE: Field repeated up to 5 times depending on the specified number of antimicrobials taken	given on admission to hospital, provide the date of admission.	
Antibiotic stewardship 1-5 (before date of interest)	Is antimicrobial prescription in line with local guidelines	Single select drop-down: Yes
NOTE: Field repeated up to 5 times depending on the		No Unknown

specified number of	
antimicrobials taken	

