#### Laboratory specimen collection, transport and analysis

No additional samples – either clinical or screening – will be collected for this survey. Patients included who do not have a CPE result will be assumed to be negative.

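### For exposures counted since admission, the date of interest closes the window at different points for cases and non-cases, so the planned crude odds ratios depart from 1 with no true association

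*Protocol*

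**What the plan says.** Appendix 1 of the protocol, in the section on data collected once per patient, defines one mandatory date per patient: "Date of interest to which exposure questions relate". The first rule that applies sets it:

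- one screen: "Date of screening test (if single test", whatever the result;
- several screens, at least one positive: "If any positive, date of first positive screen OR";
- several screens, none positive: "If all negative, date of most recent screen";
- no screen: "Today's date if never screened".

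The section on laboratory specimens adds: "Patients included who do not have a CPE result will be assumed to be negative". Never-screened patients without a clinical CPE result therefore enter as non-cases anchored at the survey.

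Three exposure items run from admission to this date. One asks: "Has the patient undergone endoscopy since admission to the Trust, on or prior to the date of interest". Major surgery is asked in the same way, and so are antimicrobials given this admission but stopped before the date of interest.

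The Data analysis section plans odds ratios with 95% confidence intervals, "using univariable, and if required, multivariable analysis". It names no adjustment for, or matching on, time from admission to the date of interest.

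**The concern.** For these three items the length of the exposure window depends on the outcome. Among repeatedly screened patients, a case's window closes at the earliest qualifying date and a non-case's at the latest available one. A never-screened non-case has the longest window that the stay allows. A longer window gives more chance of having had an operation, an endoscopy or a course of antibiotics, whatever the CPE status.

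One of the protocol's six objectives is to learn which procedures and antimicrobials are associated with CPE, and the Background says that the data will inform prevention strategies. A crude odds ratio that mainly reflects window length could make a real risk factor look protective.

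**Working it through.** **Figures in the plan.** The protocol gives no figure for the anchor rule or for the odds ratios. Its sample size matters only for the number of cases. For adults at 1% ± 1%, with N = 4090 beds, design effect 2 and z = 1.96:

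n = 2 × 4090 × 0.0099 / [(0.01/1.96)² × 4089 + 0.0099] = 80.98 / 0.1163 = 696.1, rounded up to 697; 697 × 1.10 = 767, as stated.

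At the assumed 0.5–1% prevalence this gives 767 × 0.005 = 3.8 to 767 × 0.01 = 7.7, or about 4 to 8 adult cases.

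**Closed form.** Let an exposure start at a constant rate h per day, unrelated to CPE. The odds of having been exposed by day t are exp(ht) − 1. With cases anchored at day a and non-cases at day b, the odds ratio under no association is [exp(ha) − 1] / [exp(hb) − 1]. The values of h, a and b are assumptions.

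- a = 2, b = 9: h = 0.02 gives 0.0408/0.1972 = 0.21; h = 0.05 gives 0.1052/0.5683 = 0.19.
- a = 5, b = 9: h = 0.02 gives 0.1052/0.1972 = 0.53; h = 0.05 gives 0.2840/0.5683 = 0.50.

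**Simulation under no association.** There were 2,000,000 patients per setting, and the protocol's own anchors were applied. Assumptions: mean of 14 days in ICU at survey (varied 7 to 28; exponential, gamma or lognormal), 3 earlier hospital days on average, exposure rate 0.02 to 0.10 per day, and cases found by screening. Exposed means at least one event between admission and the date of interest. "Imported" means CPE present on admission.

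Admission screen plus weekly screens (base case: exponential stay, mean 14 days, h = 0.05):

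| CPE source | Days counted, cases v non-cases | Null odds ratio | Range over other settings |
|---|---|---|---|
| All imported | 3.0 v 13.8 | 0.23 | 0.11–0.43 |
| Half imported | 10.7 v 13.7 | 0.73 | 0.49–1.16 |
| All acquired | 20.5 v 13.7 | 1.99 | 1.27–4.81 |

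In the first row, 13.3% of cases and 40.2% of non-cases are exposed: (0.133/0.867) / (0.402/0.598) = 0.153/0.672 = 0.23.

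Admission screen only, imported CPE, h = 0.05, by share of patients screened: 100%, 1.01; 75%, 0.61; 50%, 0.42; 25%, 0.29. The departure here comes wholly from unscreened patients being anchored at the survey.

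**What removes it.**

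- Stratifying on days from admission to date of interest (Mantel-Haenszel) returned 0.95 to 1.07 in every setting.
- Anchoring everyone at the survey day does not. The crude null odds ratio is about 1.0 if all CPE is imported, 1.3 to 2.1 with half acquired and 1.7 to 7.4 with all acquired.
- One term for days in a logistic model with CPE as outcome does not. In separate null runs a linear term left 0.90 to 1.55 and a log term 0.42 to 1.01. In a further set, linear or log terms left 0.81 to 1.39, while stratifying on day of stay gave 0.94 to 1.05.

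**The case against.** **Scope.** A reader might infer that all the planned odds ratios are affected. They are not. Carbapenems and third-generation cephalosporins use fixed four-week and one-year windows, and chemotherapy and haemodialysis use four weeks. Device items record status on or just before one day. Travel and overseas healthcare are asked over 12 months before admission, and sex and ethnicity have no window. The length argument reaches only the three since-admission items. This stands.

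**Single screens.** A patient screened once is anchored at that screen whatever the result, and with one admission screen for everyone the null odds ratio was 1.01. This stands as a condition. But Appendix 1 itself expects screening policy, frequency and compliance to differ between trusts and units, and no extra screening is done. Uniform single screening cannot be assumed.

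**Cause.** A reader might blame the first-positive rule for odds ratios above 1. The documents do not support that. In that setting cases have the longer windows, because CPE acquired in hospital takes time. Moving everyone to the survey day makes it worse, and anchoring at first positive properly excludes exposure after detection. What is missing is a comparable anchor, or control of time at risk, for non-cases.

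**Old positives.** It is also tempting to say that a first positive from an earlier admission leaves an empty window. The protocol does not say that screens from earlier admissions count, and it records previous CPE and its date in separate fields. That reading is possible but not established.

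**Analysis-plan detail.** Covariates are commonly left to an analysis plan, and one may exist unseen. Likewise, the protocol does not state that imported and acquired cases will be pooled; that would be inferred from silence. But the asymmetric anchor and the univariable odds ratios are stated in this document, and together they give a wrong answer for these items.

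**Precision.** With 4 to 8 adult cases, random error will be large. That limits what can be learned, but wide intervals would still be centred on the wrong value.

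**Conclusion.** The point holds for major surgery, endoscopy and antimicrobials stopped earlier in the admission. Unless screening is a single test at the same point of stay for everyone, their crude odds ratios depart from 1 with no association. They fall below 1 when cases are mostly found on admission. They can exceed 1 when cases are acquired during long stays, which is ordinary time-at-risk confounding that the plan also leaves uncorrected. In a few mixed settings the two cancel (0.99 to 1.02).

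The direction is therefore not fixed, and the size rests on assumed stay, screening and exposure rates. Prevalence, the survey's stated aim, is not affected. Severity is moderate.

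**What to change.** Keep the first-positive anchor for cases. In the Data analysis section:

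1. State that odds ratios for the three since-admission exposures will compare cases with non-cases at the same day of stay, by matching or stratifying on days from trust admission to date of interest. Say that a single linear or log term for days does not replace this.
2. Do not report crude odds ratios for these exposures as associations.
3. As a secondary analysis, use the CPE-on-admission fields to describe cases positive at or before trust admission separately, and leave them out of the in-hospital exposure comparison. The admission-screen field is "unknown" where no screen was done, so this split will be incomplete.

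No new data are needed: trust admission date and date of interest are both mandatory fields. The cost is fewer usable cases and wider intervals. With about 4 to 8 adult cases expected, some models may not be estimable, and the report should then give counts only.
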